The time in weeks from randomization until premature discontinuation from study up to Week 8 will be displayed using a Kaplan-Meier curve. This curve will be provided for subjects in TRT and CTL groups based on all subjects randomized. Subjects who do not discontinue the study within the specified time window will be presented as censored at the date of their Week 8 visit. Subjects in TRT group that missed their Week 8 visit but did not discontinue will be censored at the target day of the Week 8 visit (i.e. Day 57 after last injection in treatment Cycle 1). For subjects who attended only visits up to Week 8 with date of last contact after Week 8, the date of discontinuation will be set to the date of the Week 8 visit.

The time in months from first treatment until premature discontinuation from study will be described by a second Kaplan-Meier curve for the TRT and DTRT groups in SP. Subjects who complete the study will be presented as censored at end of study.

Visit attendance (subjects expected at visit, subjects with visit performed on-site, subjects with visit performed virtually, subjects with missed visit due to COVID-19 pandemic or other reasons, subjects discontinued) will be presented in a frequency table for various treatment groups (i.e., TN, TC, TRT, CDTN, CDTC, CDTRT) based on all randomized subjects.

For 'Study discontinued', the cumulative number of subjects who discontinued the study before the respective visit will be displayed. For 'Subjects expected at visit', the following visits are defined as expected for all randomized subjects: Screening visit, initial treatment visit V1-a, V1-b, V2-a, V3 – V7-a, V8, V9 for TRT subjects; and Screening visit, visits C1-a, C1-b, C2-a, C3 and all following visits for CDTRT subjects, as defined in the visit schedules in the CSP column for TRT subjects and column for CDTRT subjects). Visits V2-b/C2-b and V2-c/C2-c are

only expected for subjects receiving an optional touch-up at visit V2-a/C2-a. In case of retreatment at visit V7-a for TRT subjects, follow-up visits V7-b and V7-c are also expected. For subjects who discontinue the study, the end of study visit V9/C7 is expected. Visits after premature discontinuation are generally not expected. The number of 'Subjects expected at visit' is thus calculated as number of randomized subjects – the number of subjects discontinued before the respective visit.

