Percentages of 'Visit performed' (total) will be calculated relative to the number of subjects expected at the respective visit.

For columns relating to 'Subjects expected at visit', 'Study discontinued', 'Visit performed' (regularly on-site, virtually due to Coronavirus disease 2019 (COVID-19) pandemic) and 'Visit not performed' (total, due to COVID-19 pandemic, due to other reasons), only absolute numbers will be displayed. All performed and all not performed visits until regular study completion or premature discontinuation (as applicable for the respective subject) will be listed. Flags will also be included for visits performed virtually, visits not performed due to COVID-19 pandemic and visits not performed due to other reasons.

Protocol Deviation

The absolute and relative frequencies of major protocol deviations and other reasons for exclusion from the PP population will be tabulated, based on all randomized subjects for groups TN, TC, TRT, CTL and overall.

Additionally, major protocol deviations and other reasons for exclusion from the PP population related to COVID-19 pandemic will be presented in a separate table. For this purpose, each protocol deviation will be categorized whether it was related to the COVID-19 pandemic or not.

Minor protocol deviations will be listed only.

A listing of all documented impacts of COVID-19 pandemic on study conduct (incl. disruptions and modifications not constituting protocol deviations) will be provided. This listing will present investigational site identifier, randomized treatment group and information on impact of COVID-19 pandemic for all randomized subjects. In case the study conduct was impacted by COVID-19 pandemic, classified disruption or modification (e.g. visit performed virtually, time schedule deviation) and details on disruption or modification will be presented.

Demographic data and baseline characteristics

Demographic data (age, age category, sex, ethnicity, race and Fitzpatrick skin type) as well as weight, height and BMI and MIHAS baseline score as assessed by the blinded evaluator will be summarized by various treatment groups (i.e., TN, TC, TRT, CDTN, CDTC, CDTRT) and overall for the ITT, SP, PP populations and for all randomized subjects. Fitzpatrick skin type will additionally be categorized into type I-III and type IV-VI. Age will additionally be presented in categories of "< 45 years" and " \geq 45 years".

Previous and concomitant medication and non-drug treatment

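### The SAP's formula for the number of subjects expected at a visit contradicts its own visit rules, distorting attendance percentages at V2-b/c, C2-b/c, V7-b/c and V9/C7

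*SAP*

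**What the plan says.** The visit-attendance text stands under Disposition of subjects in the SAP, which follows Section 6.2.1 in the public copy. It first lists the visits expected of every randomized subject. For TRT these include the injection visits V1-a, V2-a and V7-a and the final visit V9. For CDTRT they include C1-a, C2-a and the later visits through C7.

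It then adds rules for particular visits:

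- V2-b/c and C2-b/c carry a condition: they are "only expected for subjects receiving an optional touch-up at visit V2-a/C2-a".
- V7-b/c are added only for those TRT subjects who were retreated at V7-a.
- The final visit stays due for those who leave early: "For subjects who discontinue the study, the end of study visit V9/C7 is expected".
- Other visits that fall after a subject has left are, as a general rule, not counted as due.

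Directly afterwards it states that the number expected "is thus calculated as number of randomized subjects – the number of subjects discontinued before the respective visit". For the discontinuation column, "the cumulative number of subjects who discontinued the study before the respective visit will be displayed". The attendance percentage is then fixed by this sentence: "Percentages of 'Visit performed' (total) will be calculated relative to the number of subjects expected at the respective visit".

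SAP Section 6.4.1 adds that subjects who stop early should have their end-of-study assessments recorded at V9 or C7, unless they are lost to follow-up.

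**The concern.** The formula is presented as following from the rules above it, but it does not carry them. It has no term for touch-up or retreatment, so subjects who never had the extra injection stay in the denominator of the follow-up visits to that injection. It also subtracts discontinued subjects at every visit, including V9/C7, where the rule says they are expected.

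What is at stake is how complete the safety follow-up after repeat injection appears. Protocol Section 13.4.3 calls for a summary of subjects expected at and attending each visit. Protocol Section 8.2 gives safety data on repeat treatment as one reason for offering retreatment, and Protocol Section 11.2.2.2.1 requires visual-function assessments at all follow-up visits. V2-b and V7-b have a target of Day 15 after the injection, and V2-c and V7-c of Day 29 (SAP Section 6.4.1). At these visits a low percentage could mean missed follow-up or simply few touch-ups. At the final visit the error runs the other way and makes attendance look better than it was.

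**Working it through.** **Inputs from the documents.** SAP Section 3 plans 100 TRT subjects (50 + 50) and 50 control subjects (25 + 25). These reproduce from the stated sizes and the 20% drop-out allowance: 80 / 0.8 = 100 and 40 / 0.8 = 50, total 150. The SAP gives no figure for the attendance table itself, so there is none to reproduce.

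**Assumptions.** The documents do not give the touch-up or retreatment share, the number discontinued by each visit, or the share of discontinued subjects who attend V9/C7. Ranges are shown. The 20% allowance was made for the Week 8 primary tests; using it at V9 is a further assumption.

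**1. Conditional follow-up visits (V2-b/c, C2-b/c, V7-b/c).** Let N be the number randomized, D the number discontinued before the visit, and s the share of remaining subjects who were touched up or retreated. Suppose every eligible subject attends.

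- Formula: s(N − D) / (N − D) = s.
- Visit rules: s(N − D) / s(N − D) = 100%.

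TRT, N = 100, D = 0:

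| Share s | Attend | Formula | Visit rules | Expected minus performed, by formula |
|---|---|---|---|---|
| 25% | 25 | 25/100 = 25% | 25/25 = 100% | 75 |
| 50% | 50 | 50/100 = 50% | 50/50 = 100% | 50 |
| 75% | 75 | 75/100 = 75% | 75/75 = 100% | 25 |

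Under full attendance the reported figure is just the touch-up or retreatment share. The two agree only when s = 100%. If visits not performed are derived as expected minus performed, the last column counts visits that were never due.

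**2. Injection visits (V2-a, C2-a, V7-a).** These are on the list for all randomized subjects, so the rules also give N − D. Formula and rules agree.

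**3. Final visit (V9/C7).** Let m be the number of non-discontinued subjects who miss the visit, and e the number of discontinued subjects who attend it. Performed = N − D − m + e.

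- Formula, with all D subtracted: (N − D − m + e) / (N − D) = 1 + (e − m) / (N − D). This exceeds 100% whenever e > m.
- Visit rule, with discontinued subjects expected: (N − D − m + e) / N. This cannot exceed 100%.

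TRT, N = 100, D = 20:

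| e (of 20) | Formula, m = 0 | Rule, m = 0 | Formula, m = 4 | Rule, m = 4 |
|---|---|---|---|---|
| 5 | 85/80 = 106.3% | 85% | 81/80 = 101.3% | 81% |
| 10 | 90/80 = 112.5% | 90% | 86/80 = 107.5% | 86% |
| 15 | 95/80 = 118.8% | 95% | 91/80 = 113.8% | 91% |
| 20 | 100/80 = 125.0% | 100% | 96/80 = 120.0% | 96% |

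With D = 10 and m = 0, e = 5 gives 95/90 = 105.6% and e = 10 gives 100/90 = 111.1%. At C7 with N = 50 and D = 10, the same proportions give the same percentages; for example, e = 5 gives 45/40 = 112.5%.

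**4. Milder reading of the final visit.** Suppose a subject who attends an early-termination V9 is not counted as discontinued before it. The denominator becomes N − (D − e). With D = 20, e = 10 and m = 0 this is 90/90 = 100%, against 90/100 = 90% under the rule. Nothing exceeds 100%, but the 10 discontinued subjects who did not attend have left the denominator although the rule expects them.

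**The case against.** The best defence is that the formula was never meant to override the explicit rules. It comes straight after the sentence on visits following discontinuation, and may only draw the consequence of that sentence for visits everyone has. The mock tables, which SAP Section 1 makes the programming specification, are not in the public documents and may hold the right denominator. SAP Section 6 also asks for a footnote where a denominator is not obvious. This reading is plausible, so a wrong table is not certain. But the text does not limit the formula, and a programmer is left with two conflicting instructions.

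Three stronger readings are tempting, and the documents do not support them.

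- A reader might infer that every touch-up and retreatment visit is affected. The injection visits themselves are not.
- A reader might infer that attendance above 100% must appear at V9/C7. It needs early-termination attendees to count as discontinued before that visit, which the SAP does not settle, and more of them than the non-discontinued subjects who miss it.
- A reader might infer that real gaps in follow-up could not be found. The SAP also plans subject-level listings of performed and not-performed visits with reasons, counts of visits not performed, tables of subjects who received touch-up and retreatment, and discontinuation reasons. A reader could largely rebuild the right denominator from these. That does not make the tabulated percentage correct.

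It is also fair to say that keeping every discontinued subject in the V9/C7 denominator is not obviously right, because SAP Section 6.4.1 exempts those lost to follow-up from the end-of-study assessments.

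**Conclusion.** The contradiction is in the current SAP text, and its direction is clear. Applied as written, the formula understates attendance at V2-b/c, C2-b/c and V7-b/c whenever some remaining subjects had no touch-up or retreatment. Under full attendance the shortfall equals the share of remaining subjects without the extra injection: 75, 50 or 25 percentage points in the assumed cases.

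At V9/C7 it overstates attendance relative to the stated rule. With 20 of 100 discontinued and all others attending, the formula gives 106.3% to 125.0% where the rule gives 85% to 100%, if 25% to 100% of discontinued subjects attend and are counted as discontinued beforehand. The counts are illustrative. If subjects lost to follow-up were exempt, the rule's own percentage would be higher than shown.

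The importance is minor. The expected counts, one percentage and possibly the not-performed counts of one descriptive table are affected. The primary analysis, type I error, power and adverse-event incidences do not depend on it.

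**What to change.** Replace the single formula with denominators by visit type:

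- **Visits expected of all subjects, other than V9/C7:** randomized minus discontinued before the visit, as now.
- **V2-b/c and C2-b/c:** subjects with a touch-up, minus those discontinued before the visit.
- **V7-b/c:** subjects retreated at V7-a, minus those discontinued before the visit.
- **V9/C7:** either keep discontinued subjects in the denominator and state how those lost to follow-up are counted, given Section 6.4.1; or show early-termination visits on a separate row with their own denominator.

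The SAP should also say whether a subject attending an early-termination V9/C7 counts as discontinued before that visit. The cost is a few lines of SAP wording and the denominator in one table. The data needed are already collected.

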6.4 Special Statistical/Analytical Issues

6.4.1 Discontinuations and Missing Data

Subjects discontinuing the study prematurely should perform and record end-of-study assessments at V9 (subjects in TRT) or at C7 (subjects in CDTRT), unless they are lost to follow-up. Effectiveness data of discontinued subjects collected at these visits will therefore be analyzed under the study visit which is closest to the recorded V9/C7 date. This will be based on the assessment date relative to last treatment and treatment cycle, using the following visit windows:

Case 1: Subject without touch-up

Timepoint	Subject Status	Window Start	Target Day of Visit	Window End
Cycle 1: V1-b/C1-b		Day 2 (after initial treatment)	Day 15 (after initial treatment)	Day 22 (after initial treatment)
Cycle 1: V2-a/C2-a		Day 23 (after initial treatment)	Day 29 (after initial treatment)	Day 43 (after initial treatment)
Cycle 1: V3/C3		Day 44 (after initial treatment)	Day 57 (after initial treatment)	Day 71 (after initial treatment)

Timepoint	Subject Status	Window Start	Target Day of Visit	Window End
Cycle 1:		Day 72 (after initial	Day 85 (after initial	Day 127 (after initial
V4/C4		treatment)	treatment)	treatment)
Cycle 1:		Day 128 (after initial	Day 169 (after initial	Day 211 (after initial
V5/C5		treatment)	treatment)	treatment)
Cycle 1:		Day 212 (after initial	Day 253 (after initial	Day 295 (after initial
V6/C6		treatment)	treatment)	treatment)
Cycle 1: C7		Day 296 (after initial treatment)	Day 337 (after initial treatment)	Open end
Cycle 1: V7-a	No retreatment at V7-a	Day 296 (after initial treatment)	Day 337 (after initial treatment)	Day 365 (after initial treatment)
Cycle 1: V8	No retreatment at V7-a	Day 366 (after initial treatment)	Day 393 (after initial treatment)	Day 449 (after initial treatment)
Cycle 1: V9	No retreatment at V7-a	Day 450 (after initial treatment)	Day 505 (after initial treatment)	Open end
Cycle 2: V7-a	Retreatment at V7-a	No end of study data will be assigned to this visit as subject received retreatment at this visit.		
Cycle 2: V7-b	Retreatment at V7-a	Day 2 (after retreatment)	Day 15 (after retreatment)	Day 22 (after retreatment)
Cycle 2: V7-c	Retreatment at V7-a	Day 23 (after retreatment)	Day 29 (after retreatment)	Day 43 (after retreatment)
Cycle 2: V8	Retreatment at V7-a	Day 44 (after retreatment)	Day 57 (after retreatment)	Day 113 (after retreatment)
Cycle 2: V9	Retreatment at V7-a	Day 114 (after retreatment)	Day 169 (after retreatment)	Open end

Case 2: Subject with touch-up

Timepoint	Subject Status	Window Start	Target Day of visit	Window End	
Cycle 1:		No end of study data will be assigned to this visit as subject received			
V1-b/C1-b		touch-up after this visit.			
Cycle 1:		No end of study data will be assigned to this visit as subject received touch-up at this visit.			
V2-a/C2-a					
Cycle 1:		Day 2 (after touch-	Day 15 (after touch-	Day 22 (after touch-	
V2-b/C2-b		up)	up)	up)	
Cycle 1:		Day 23 (after touch-	Day 29 (after touch-	Day 43 (after touch-	
V2-c/C2-c		up)	up)	up)	
Cycle 1:		Day 44 (after touch-	Day 57 (after touch-	Day 71 (after touch-	
V3/C3		up)	up)	up)	
Cycle 1:		Day 72 (after touch-	Day 85 (after touch-	Day 127 (after touch-	
V4/C4		up)	up)	up)	
Cycle 1:		Day 128 (after touch- up)	Day 169 (after touch- up)	Day 211 (after touch- up)	

Timepoint	Subject Status	Window Start	Target Day of visit	Window End
V5/C5				
Cycle 1: V6/C6		Day 212 (after touch- up)	Day 253 (after touch- up)	Day 295 (after touch- up)
Cycle 1: C7		Day 296 (after touch- up)	Day 337 (after touch- up)	Open end
Cycle 1: V7-a	No retreatment at V7-a	Day 296 (after touch- up)	Day 337 (after touch- up)	Day 365 (after touch- up)
Cycle 1: V8	No retreatment at V7-a	Day 366 (after touch- up)	Day 393 (after touch- up)	Day 449 (after touch- up)
Cycle 1: V9	No retreatment at V7-a	Day 450 (after touch- up)	Day 505 (after touch- up)	Open end
Cycle 2: V7-a	Retreatment at V7-a	No end of study data will be assigned to this visit as subject received re-treatment at this visit.		
Cycle 2: V7-b	Retreatment at V7-a	Day 2 (after retreatment	Day 15 (after retreatment)	Day 22 (after retreatment)
Cycle 2: V7-c	Retreatment at V7-a	Day 23 (after retreatment	Day 29 (after retreatment)	Day 43 (after retreatment)
Cycle 2: V8	Retreatment at V7-a	Day 44 (after retreatment	Day 57 (after retreatment)	Day 113 (after retreatment
Cycle 2: V9	Retreatment at V7-a	Day 114 (after retreatment	Day 169 (after retreatment)	Open end

If based on the above windows, a V9/C7 end of study assessment would be assigned to a timepoint for which a regular visit was performed, then the data from the respective visit will be used for analysis, and the V9/C7 data will only be listed. Also, no data recorded under V9/C7 (end of study) visit will be assigned to a visit with initial, touch-up or retreatment performed.

If V8/C6 was performed and the subject later prematurely discontinued the study, V9/C7 visit will be analyzed as documented.

Effectiveness data

Methods for handling of missing primary effectiveness endpoint data are described in Section 6.1.1.

Handling of missing scores of FACE-Q Satisfaction with Eyes scores is described in Section 6.1.2. Handling of missing scores of FACE-Q Appraisal of Lower Eyelids is described in Section 6.1.3.

For remaining endpoints, observed cases will be analyzed, if not otherwise specified.

Safety data

For the imputed analysis start date of AEs (variable ASTDT in the ADaM domain ADAE), imputation rules related to any cycle are described in Section 6.

Missing data of the worst outcome will be imputed by "unknown". For any other missing data of AEs, a worst-case strategy will be applied for all analysis tables. The intensity will be imputed by worst intensity "severe" and the causal relationship will be imputed by the worst causal relationship "related".

Rules for handling missing eDiary entries are described in Section 6.2.

6.4.2 Interim Analyses

No interim analyses are planned.

6.4.3 Multiple Comparisons/Multiplicity

Based on the primary effectiveness endpoint, four hypothesis tests will be performed. To control for multiplicity, a hierarchical-testing procedure will be performed (see Sections 6.1.1.1 and 6.1.1.3).

6.4.4 Examination of Subgroups

Subgroup analyses are specified in Section 6.1.1.3 for the primary effectiveness endpoint, for the secondary effectiveness endpoints in Section 6.1.2, and for IPR endpoints in Section 6.1.1.3

Subgroup analyses for safety endpoints are described in Section 6.2.1 for TEAE and in Section 6.2.2 for CTR analyses.

6.4.5 Pooling of Sites

Pooling of investigative sites will be performed according to the algorithm below and only for the usage as a factor in the Multiple Imputation model and in the logistic regression model. For the Multiple Imputation model, pooling will be performed for TRT and CTL groups separately. If convergence problems are observed in either of the two models, the following steps will be performed.

- The site with the lowest number of randomized subjects will be pooled with the site with second lowest number of subjects. Regarding the logistic regression model, if two or more sites with the same number of subjects are suited for pooling, the site with the lowest number of subjects in the control group will be pooled. If two or more sites with the same number of subjects and same number of subjects in the control group (only applicable for logistic regression model) are suited for pooling, then the site to be pooled will be chosen randomly among all suited sites.
- Logistic regression/Multiple Imputation will be re-run with pooled site as factor.
- 3. If convergence problems are resolved, no further pooling of investigative sites will be performed. Otherwise, steps 1) and 2) above will be repeated until convergence problems resolve. If pooling of sites does not resolve convergence problems (unless all sites are pooled), site will be completely removed from the model.

8 References

 Anne Lott & Jerome P. Reiter (2018): Wilson Confidence Intervals for Binomial Proportions With Multiple Imputation for Missing Data, The American Statistician, DOI: 10.1080/00031305.2018.1473796 [2] Yulia Sidi & Ofer Harel (2021): Difference Between Binomial Proportions Using Newcombe's Method With Multiple Imputation for Incomplete Data, The American Statistician, DOI: 10.1080/00031305.2021.1898468
